10. MEASUREMENT OF EFFECT

The effect of naltrexone (and placebo in the control group) will be defined as a difference (in raw FACIT score) between the pre-randomization FACIT and the follow-up FACIT.

FACIT-fatigue subscale: This 13-item self-report scale measuring fatigue and functional impairment as a result of fatigue has been validated in cancer patients.⁴² It shows strong internal consistency (coefficient alpha range = 0.93-0.95) and test-retest reliability of 0.82⁴³. The scale is reverse-scored and the range is 0 (maximum fatigue) - 52 (minimum fatigue). According to ICD-10 criteria, a score ≤ 34 indicates significant cancer related fatigue. A methodologically robust review of validated cancer-specific fatigue scales recommends the FACIT-fatigue subscale as the preferred outcome measure for research.⁴⁴

10.1 Other Response Parameters

Depression, anxiety, subjective cognitive function, sleep quality, insomnia, and quality of life outcome measures including pain will be assessed at study visits using the self-report measures listed below.

GAD7: (4 minutes) The Generalized Anxiety Disorder scale (GAD-7) is a 7-item self-report anxiety questionnaire which was initially validated in primary care populations; it has also been shown to be reliable and valid in the general population⁴⁵. Of note, prior literature suggests that high baseline anxiety may be a risk factor for radiotherapy-emergent fatigue in breast cancer patients¹¹

Cognitive and Physical Functioning Scale (CPFQ) (5 minutes): The CPFQ assesses both cognitive and physical functioning of individuals with mood and anxiety disorders. The CPFQ is a 7-item questionnaire that uses a 1-6 scale to measure impairment over the past month. The total score ranges from 6-42 points.

Insomnia Severity Index (ISI): (4 minutes) The ISI is a subjective self-report assessment of sleep quality, restedness upon arising, daytime fatigue, attention/concentration and disturbances in relationships and mood. It is reliable and valid and has 7 items that use a 5-point Likert-style scale. Scores can range from 0 to 28. Of the 7 questionnaire items, 3 assess the severity of insomnia and 1 question each assesses satisfaction with current sleep pattern, sleep interference,

"noticeability" of sleeping problem to others, and concern about sleeping problems.⁴⁶

Pittsburgh Sleep Quality Index (PSQI): (6 minutes) The PSQI is a widely used 19-item self-rated measure of sleep quality occurring during the one-month prior to assessment.⁴⁷ The PSQI has good test-retest reliability in healthy controls, depressed subjects, and sleep-disordered subjects.⁴⁷ The total PSQI score distinguishes healthy controls from individuals with depression and problems initiating and maintaining sleep.⁴⁷

Functional Assessment of Cancer Therapy-Breast (FACT-B): (8 minutes) The FACT-B is a 37-item self-report questionnaire intended to assess quality of life in breast cancer patients. The measure is composed of 5 subscales: physical well being (7 items), social/family well-being (7 items), emotional well-being (6 items), functional well-being (7 items), and breast cancer related items (10 items). Subjects are asked to indicate how they have felt in the past 7 days on a 5-point Likert scale ranging from 0=Not at all to 4=Very much with higher scores indicating better quality of life. The FACT-B demonstrates good internal consistency (Cronbach's $\alpha=0.88$), good discriminative validity, and is sensitive to change.⁴⁸

Functional Assessment of Cancer Therapy-Endocrine Subscale (FACT-ES): (4 minutes) Often used in combination with the FACT-B, the FACT-ES is intended to assess quality of life. Using the same 4 subscales of physical, social, emotional and functional well-being as the FACT-B, the FACT-ES contains an additional 19-item endocrine symptom subscale that assesses menopause symptoms. FACT-ES demonstrates good internal consistency, test-retest reliability, and sensitivity to change.⁴⁹

Patient Global Impression-Fatigue (PGI-Fatigue): (1 minute) This is a scale designed to assess global severity of fatigue and change in the patient's fatigue over time. This scale will be taken by the patient to assess severity of present fatigue and improvement relative to baseline state. It consists of 2 global subscales, severity of fatigue and global improvement. The clinician will determine the onset and duration for the symptoms as well as the impact of the symptoms on behavior and function in order to determine fatigue severity. The subscales are rated on 7-point scales with the range 0=not assessed to 7=Extremely ill. They have been found to be valid and reliable measures of fatigue and are validated with the CPFQ measure described above.⁵⁰

Patient Health Questionnaire (PHQ-9): (3 minutes) The PHQ-9 is the self-administered form of the Primary Care Evaluation of Mental Disorders (PRIME-MD), a widely used instrument designed to screen for psychiatric illnesses in primary-care settings. The PHQ-9 is a 9-item self-report questionnaire that assesses mood, depressive symptoms, and suicidal ideation. It is used widely as a diagnostic screening tool for major depressive disorder, and has been found to be as good as longer clinician-rated interviews in a variety of settings. If any subject indicates suicidal ideation on the PHQ-9, she will be evaluated according to the suicide protocol described above in order to determine appropriate treatment and safety measures.⁵¹

PEG: (1 minute). The PEG is an ultra-brief self-report scale measuring pain. It contains three items which assess average pain intensity (P), interference with enjoyable activities (E), and interference with general activity (G). It has been shown to have strong reliability, construct validity, and sensitivity to change in primary care and other ambulatory clinic patients.⁵²

Demographics/Patient Characteristics Form: (3 minutes) This form will be completed by the patient to capture demographic, education, and prior health information.

Clinical Variables: Radiotherapy-related information to be completed by dosimetrist or physicist.

Subject Exit Form: This form will be completed by the study coordinator to capture summary of patient participation.

11. DATA REPORTING / REGULATORY REQUIREMENTS

Adverse event lists, guidelines, and instructions for AE reporting can be found in Section 7.0 (Adverse Events: List and Reporting Requirements).

11.1 Data Reporting

11.1.1 Method

Data is collected in an independent database created by the study team.

11.1.2 Responsibility for Data Submission

Investigative sites within DF/HCC or DF/PCC are responsible for collecting data variable within the study database.

11.2 Data Safety Monitoring

The DF/HCC Data and Safety Monitoring Board (DSMB) will review and monitor study progress, toxicity, safety and other data from this study. The board is chaired by a medical oncologist from outside of DF/HCC and has external and internal representation. Information that raises any questions about participant safety or protocol performance will be addressed by the Overall PI, statistician and study team. Should any major concerns arise, the DSMB will offer recommendations regarding whether or not to suspend the trial.

The DSMB will meet twice a year to review accrual, toxicity, response and reporting information. Information to be provided to the DSMB may include: participant accrual; treatment regimen information; adverse events and serious adverse events reported by category; summary of any deaths on study; audit results; and a summary provided by the study team. Other information (e.g. scans, laboratory values) will be provided upon request.

The study statistician, [name], will conduct the planned interim efficacy analysis. The PI will maintain oversight of administrative issues related to the analysis.

11.3 Multicenter Guidelines

N/A

11.4 Collaborative Agreements Language

N/A

12. STATISTICAL CONSIDERATIONS

Entry criteria of a drop of 10 points on FACIT-fatigue subscale was selected because a change of 10 points has been shown to constitute a clinically meaningful difference on this subscale⁵³. The effect of naltrexone (and placebo in the control group) will be defined as a difference (in raw FACIT score) between the pre-randomization FACIT and the follow-up FACIT. FACIT-fatigue subscale scores are normally distributed in anemic and nonanemic cancer populations⁴², with a standard deviation of 10 points. Setting power as 0.8, and significance as 0.05, assuming a two-sided type I error, 122 patients per arm are required to detect a “difference of a difference” of at least 3.6 points on FACIT-fatigue. The 3.6 point difference was selected because it is the approximate mean of prior effect sizes utilizing FACIT-fatigue in clinical trials of erythropoietin or darbopoeitin vs. placebo. Assuming a 20% drop-out rate, approximately 150 patients per arm will be randomized.

An interim analysis will be conducted on one occasion, after collecting data for the first 75 patients in each arm. This analysis will be conducted in light of several possibilities: 1) the observed benefit of naltrexone is so promising that it would be unethical not to use it for all eligible patients, 2) the observed rate of side effects/toxicity is too high, 3) futility –it appears to be unlikely that there is a clinically significant difference between the naltrexone and placebo arms. The Haybittle–Peto boundary rule (with 0.001 significance threshold) will be employed to determine whether the trial should be stopped early. The final analysis will still use the 0.05 threshold of significance.

Futility testing will also be performed on the primary outcome at a low level (one-sided alpha 0.0025) on one occasion (after the first 75 patients are enrolled).

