1.1 Study Design

A randomized, double-blind, parallel-arm 5-week clinical trial will be used to determine the effect of naltrexone on fatigue emerging during radiation therapy for non-metastatic breast cancer (see Protocol Schema). The trial has two phases (a monitoring phase and an intervention phase) requiring two separate consents.

Monitoring phase: Prior to initiating radiotherapy, participants will be approached and consented for the monitoring phase of the study, which involves longitudinal monitoring of fatigue in order to establish whether a patient develops fatigue after starting radiation. The level of pre-radiotherapy fatigue will be obtained during the final 3 weeks before, or within 3 days, that radiotherapy is started. Participants who provide baseline data and report suicidal ideation either spontaneously or on a self-report questionnaire will be excluded from subsequent weekly monitoring of fatigue. All other participants will undergo weekly monitoring of fatigue via a brief self-report questionnaire (Functional Assessment of Chronic Illness Therapy-Fatigue Subscale; FACIT-F) once radiation therapy begins. Those whose fatigue symptoms increase above the pre-specified threshold at any point during the monitoring period will be approached about enrollment into the intervention phase of the study. The monitoring period will continue up until one month after the conclusion of radiotherapy. Radiation oncologists will refer potentially eligible patients to the monitoring phase of the study. The clinical research coordinator will be trained to administer the screening consent and will follow participants during the monitoring phase of the study and notify the radiation oncologist if fatigue emerges/worsens after radiation therapy has begun, so that participation in the intervention phase of the study can be discussed with these patients.

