The durations of most placebo-controlled trials of naltrexone for alcohol and opioid dependence have ranged from 12-52 weeks, although shorter positive trials (3-12 weeks) exist in the literature. Clinically, for treatment of alcohol and opioid dependence, an initial 4-month course of naltrexone is recommended, and the medication can be continued indefinitely in the setting of good response.²⁶ The present study differs in that the target population will receive naltrexone for radiotherapy-emergent fatigue, which has been shown in prior studies to improve spontaneously after the conclusion of radiation treatment, returning to pre-treatment levels in the majority of patients by three months after radiotherapy.^{13,15} Therefore, a 5-week trial duration will be utilized in order to minimize the possibility of missing the appropriate time period in which to demonstrate treatment effect as opposed to spontaneous recovery. Further supporting the 5-week trial duration is the observation that patients often demonstrate therapeutic benefit from naltrexone within the first few days or weeks of treatment.²⁷

Pharmacokinetics

Naltrexone has a volume of distribution of 1350 L, and is 21% protein bound. It is metabolized hepatically via dihydrodiol dehydrogenase and conjugation to its principal metabolite, 6-beta-naltrexol. It is 53-75% renally excreted, mostly as metabolites, less than 2% unchanged. The elimination half-life of 6-beta-naltrexone is 5-10 days.

Despite its hepatic metabolism, naltrexone does not interact with the cytochrome P450 enzyme system.

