3.3 Eligibility Criteria for Randomization Phase

- 3.3.1 Participants may have had prior breast surgery and/or chemotherapy.
- 3.3.2 Age \geq 18 years.

Because no dosing or adverse event data are currently available on the use of naltrexone in cancer patients <18 years of age, children are excluded from this study, but will be eligible for future pediatric trials.

- 3.3.3 Participants must have acceptable pre-treatment laboratory values as defined below:

- total bilirubin within normal institutional limits
 - AST(SGOT)/ALT(SGPT) $\leq 2.5 \times$ institutional upper limit of normal
 - creatinine within normal institutional limits
- OR
- creatinine clearance ≥ 60 mL/min/1.73 m² for patients with creatinine levels above institutional normal.
 - TSH <10 mIU/L

- 3.3.4 If child-bearing potential, willingness to use adequate contraception (hormonal or barrier method of birth control; abstinence) prior to study entry and for the duration of study participation. Should a woman become pregnant or suspect she is pregnant while she or her partner is participating in this study, she should inform her treating physician immediately.

- 3.3.5 Ability to understand and the willingness to sign a written informed consent document

- 3.3.6 Receiving radiation therapy of any type at DFCI, BWH, MGH, or affiliated network sites (including but not limited to partial breast irradiation, two-field, three-field, and four-field plans)
- 3.3.7 FACIT-F subscale score ≥ 10 pre-radiation therapy and decrease in FACIT-F of 10 points or more as compared to prior FACIT

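### The primary FACIT-F comparison is a raw change score with no covariate, although week-0 and pre-radiotherapy scores are held for every eligible randomised patient; the analysis is valid but forgoes some precision

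*Combined protocol and SAP*

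**What the plan says.** Section 12 of the combined protocol and SAP states "The effect of naltrexone (and placebo in the control group) will be defined as a difference (in raw FACIT score") between the pre-randomisation and follow-up FACIT. Section 10 gives the same definition, and section 12.1 restates it as change from randomisation to the end of the study. None of these sections names a model or a covariate for the primary comparison.

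Two FACIT-F scores exist before treatment. Section 1.1 provides for the first: "The level of pre-radiotherapy fatigue will be obtained during the final 3 weeks before, or within 3 days, that radiotherapy is started". Criterion 3.3.7 makes it a condition of randomisation: "FACIT-F subscale score ≥ 10 pre-radiation therapy and decrease in FACIT-F of 10 points or more as compared to prior FACIT". The second is the week-0 score in the intervention calendar of section 9, which the change score subtracts.

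Section 2.2 says that radiotherapy-related fatigue improves spontaneously, "returning to pre-treatment levels in the majority of patients by three months after radiotherapy", and explains the five-week duration by the need to separate treatment effect from that recovery.

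Section 12.4 puts one covariate, radiotherapy status, into a multivariate analysis, under the secondary endpoints. Section 9 lists possible covariates for the course of fatigue, and the pre-radiotherapy FACIT-F is not among them. Randomisation uses chemotherapy (section 12.3) and blocks by site (section 4.3).

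**The concern.** If patients drift back towards their pre-radiotherapy level, the depth of each patient's fall predicts how much she regains, in either arm. Take two patients at 20 at week 0, one down from 45 and the other from 30. Their falls are 25 and 10 points. With 60% recovery they would regain 0.6 × 25 = 15 and 0.6 × 10 = 6 points whatever their treatment. A raw change score leaves that 9-point difference in the error term. Adjusting for week 0 alone cannot separate these two patients, because their week-0 scores are equal.

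The entry rule does not remove this variation. It sets a minimum fall of 10, and falls above that still differ.

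At stake is precision. There is little slack in the design: 150 per arm less 20% leaves 150 × 0.8 = 120 completers, just under the 122 required.

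**Working it through.** **1. The plan's own figure.** Section 12 gives: "Setting power as 0.8, and significance as 0.05, assuming a two-sided type I error, 122 patients per arm are required to detect" a difference "of at least 3.6 points on FACIT-fatigue", with scores "with a standard deviation of 10 points". That SD is stated for FACIT-F scores and is used as the SD of change.

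- n per arm = 2 × (1.96 + 0.8416)² × 10² / 3.6² = 121.1, rounded up to 122. The stated figure reproduces.
- Power = Φ(3.6 / (SD × √(2/n)) − 1.96). With SD 10 this is 80.3% at n = 122 and 79.6% at n = 120. The second figure corresponds to "Assuming a 20% drop-out rate, approximately 150 patients per arm will be randomized".

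**2. What a covariate could do in general.** If the added covariates have (multiple) correlation R with the change, the residual SD is 10 × √(1 − R²). With 122 per arm:

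| R | Power | n per arm for 80% |
|---|---|---|
| 0 | 80.3% | 122 |
| 0.2 | 81.9% | 117 |
| 0.3 | 83.8% | 111 |
| 0.4 | 86.6% | 102 |
| 0.5 | 90.1% | 91 |

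The documents do not give R. The only correlation they report is the test-retest value of 0.82 in section 10.

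**3. A simulation with the entry rule applied.**

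- From the documents: score SD 10, test-retest 0.82 (error SD = 10 × √0.18 = 4.24), range 0-52, and entry on a pre-radiotherapy score of at least 10 and a fall of at least 10.
- Assumed: pre-radiotherapy mean 40; true fall max(N(6, 6), 0), which makes about 30% qualify and so matches section 12.2; mean recovery of the fall by the endpoint 30%, 60% or 90% (SD 20%).

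The change SD in this model is 6.0, 6.1 and 6.5. To keep the plan's SD of 10, the missing variance is added as noise unrelated to either score. The residual variance is then 100 − R² × (model SD)².

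| Mean recovery | Model SD | R², week 0 | R², both | Power, week 0 | Power, both | Added by pre-radiotherapy score |
|---|---|---|---|---|---|---|
| 30% | 6.0 | 0.04 | 0.09 | 80.8% | 81.6% | 0.8 |
| 60% | 6.1 | 0.07 | 0.17 | 81.3% | 82.8% | 1.5 |
| 90% | 6.5 | 0.12 | 0.26 | 82.3% | 84.6% | 2.3 |

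Worked example, 60% recovery, both scores: 100 − 0.17 × 6.1² = 93.7; residual SD 9.68; 3.6 / (9.68 × 0.128) − 1.96 = 0.945; Φ(0.945) = 82.8%.

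**4. Lower reliability.** At an assumed reliability of 0.50 the model's change SD is already about 9, so little noise has to be added. Both scores then give about 85-90%. Most of this comes from week 0, and the pre-radiotherapy score adds about 1 point.

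**5. A second model.** Here follow-up moves a fraction L of the way back to the observed pre-radiotherapy score, with the change SD held at 10. Assumed: pre-radiotherapy means 40-42, monitoring means 34-36, correlation before selection 0.5-0.7.

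| L | Power, both scores |
|---|---|
| 0 | 80% |
| 0.25 | 80.6-80.8% |
| 0.5 | 81.6-82.6% |
| 0.75 | 83.3-85.5% |
| 1 | 85.8-89.3% |

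At L = 1, week 0 alone gives 81.0-82.7%, so most of the gain there belongs to the pre-radiotherapy score. That is a ceiling, because it treats the measured score as the exact level to which every patient returns, with the return complete by the endpoint.

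**The case against.** The strongest reply is that nothing is broken. Randomisation makes the raw difference unbiased, its type I error already allows for chance imbalance in depth of fall, and 122 per arm gives the stated power on the plan's inputs. All of that stands.

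A second reply is that much of the gain is the familiar advantage of adjusting for the week-0 score and has little to do with the pre-radiotherapy one. This also stands in part. In step 3 week 0 supplies somewhat under half of the gain, and at reliability 0.50 it supplies most of it. In an unselected model with equal SDs and a week-0 to follow-up correlation of 0.5, week 0 alone reaches 90.1%, and the second score can add as little as 0.1 point.

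A third reply is timing. Section 2.2 places recovery at three months after radiotherapy, whereas study treatment ends at week 5 and patients may be randomised during radiotherapy. Recovery of 90% by the endpoint is therefore a high case.

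Finally, the comparator in 3.3.7 is loosely worded and may not be the pre-radiotherapy score. That would change the simulated entry rule. It would not change the availability of the score, because the first half of the criterion requires it.

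A reader might go further the other way and infer a gain of 4 to 10 points by putting the R² values of 0.09, 0.17 and 0.26 straight into the SD-10 power formula, which gives 84%, 87% and 90%. The documents do not support this. Those R² values belong to a model with a change SD of 6.0-6.5, where the raw comparison already has 99.2-99.7% power. Carrying them to SD 10 assumes that the missing variance is just as predictable, and nothing in the plan says so.

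**Conclusion.** The point holds as forgone precision. Both scores are available, the plan's own account of recovery makes the pre-radiotherapy one prognostic, and neither is used as a covariate. With test-retest 0.82 and an SD of change of 10, using both would raise power from 80% to about 82-85% for 30-90% recovery, of which the pre-radiotherapy score adds about 1 to 2 points beyond week 0. At reliability 0.50 the total is about 85-90%, mostly from week 0. The gain is near zero if little recovery has occurred by the endpoint, and larger than these ranges for the pre-radiotherapy score only if recovery to the measured level is nearly complete.

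All sizes rest on assumed recovery fractions, means and reliabilities, because the plan gives no correlation with the change. A reader might infer that the trial is underpowered or that 122 is wrong. Neither follows, since the stated power reproduces for the raw change score.

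**What to change.** In section 12, before unblinding, name the primary analysis as a linear model (ANCOVA) of FACIT-F change, or equivalently of the follow-up score, on arm, week-0 FACIT-F and pre-radiotherapy FACIT-F, with the randomisation factors (chemotherapy and site). Report the treatment effect in FACIT-F points with its confidence interval. State that the pre-radiotherapy value is the monitoring-phase baseline score used for the first half of 3.3.7. Point sections 10 and 12.1 to the same model.

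The cost is a sentence or two of text. No new data are needed, each score uses one degree of freedom out of about 244 patients (2 × 122), and the sample size can stay as it is. The timing matters: a covariate chosen after unblinding would look data-driven.

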Intervention phase: Radiation oncologists will consent patients who develop treatment-emergent fatigue developing during or within one month after completion of radiation therapy and who are interested in participating in the intervention phase of the study. After informed consent is obtained and final eligibility determination is complete, participants will have 5 study visits: one at study entry to initiate treatment (week 0), one to rule out any contraindication to the scheduled dose escalation (week 1), one at the conclusion of medication treatment for treatment outcome assessment and safety monitoring (week 5), and the last at four weeks after discontinuation of study drug vs. placebo (week 9). All intervention visits have a window of ± 7 days.

Study treatment: The treatment schedule includes a daily dose of double-blinded naltrexone vs. placebo for 5 weeks. Treatment will be initiated at 25 mg/day (or equivalent placebo) during the first week to improve tolerability. The dose will be escalated to 50 mg/day (or equivalent placebo) after one week barring significant early improvement in fatigue or adverse events precluding dose escalation, and participants will continue to take 50 mg/day (or 25 mg/day if dose is not escalated) for 4 weeks to complete a 5-week treatment period.

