5.3 Agent Administration

All participants will be instructed to swallow the double-blinded medications in the morning with food.

Monitoring and Intervention Phases: Visit Breakdown – Refer to study calendar in section 9.

Monitoring Phase (duration: 1-10 weeks):

- Visit 1: Collection of baseline data.
 - a. Patient demographic information and clinical characteristics will be collected by self-administered surveys.

- b. Completion of self-reported fatigue, anxiety, depression, sleep and quality of life questionnaires.
- Visits 2-10 (in person or by phone): Monitoring procedures including completion of self-reported fatigue and other quality of life questionnaires

The occasional mis-timed (or missed) FACIT does not automatically constitute a protocol violation. However, in order to remain in compliance with the protocol, a minimum of 4 FACITs is needed for partial breast irradiation patients, 5 FACITs for hypofractionation patients, and 7 FACITs for standard (6 week) fractionation patients. The monitoring phase terminates either at entrance into the intervention phase of the study, or at 4 weeks after the conclusion of radiation therapy, whichever comes first.

Intervention Phase (duration 5 weeks):

- Visit 1a:
 - a. consent for trial;
 - b. review of concomitant medications;
 - c. complete baseline fatigue questionnaire (unless completed within past week)—may be completed at Visit 1b;
 - d. complete anxiety, depression, sleep and quality of life questionnaires (unless completed within past week)—may be completed at Visit 1b;
 - e. urine HCG only in women with reproductive potential; blood draw to evaluate LFTs, Hct, BUN/Cr unless results are available within the previous month;
 - f. specimens will be banked for future analysis of fatigue-related genetic polymorphisms and inflammatory biomarkers (participants can opt out of specimen banking)
- Visit 1b: laboratory study results reviewed to confirm eligibility; receive medication bottles and medication diary; receive patient education sheet on contraindicated medications and safety card (see Appendix A); Visit 2 (one week after starting study drug vs. placebo): fatigue/response and adverse event assessment for dose escalation, review of concomitant medications, fatigue assessment

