12.1 Study Design/Endpoints

The study is a randomized placebo-controlled trial. The primary outcome measure will be change score on the FACIT-fatigue subscale from randomization to the end of the study. Exploratory endpoints include changes in sleep continuity (sleep efficiency, total sleep time, sleep latency), quality-of-life measures, depression, anxiety, and subjective cognitive function.

Analysis of both the primary and exploratory endpoints will be by modified intention to treat. The mITT analysis (for both primary and exploratory endpoints) will be a per-protocol analysis; only patients who complete the entire trial according to the protocol will be counted towards the final results.

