12.4 Analysis of Secondary Endpoints

Secondary (exploratory) endpoints (changes in sleep continuity (sleep efficiency, total sleep time, sleep latency), quality-of-life measures, depression, anxiety, and subjective cognitive function) will be analyzed by modified intention to treat. Since no pre-existing data describes the magnitude of associations of our exploratory outcomes with naltrexone use in this population, we are unable to speculate on the statistical power required to detect an effect. Any relevant associations and their statistical significances will be calculated using descriptive statistics. In addition, radiation therapy status (currently receiving RT vs. recently completed RT) will be included as a covariate in the multivariate analysis.

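### The primary comparison is of raw FACIT-F change with no baseline covariate, but the trial is sized with the SD of a single score; the 80% power rests on an unstated SD of change of about 10, and adjusting for week-0 FACIT-F would be more precise at almost no cost.

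*Combined protocol and SAP*

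**What the plan says.** Section 12 states that the effect in each arm "will be defined as a difference (in raw FACIT score) between the pre-randomization FACIT and the follow-up FACIT", and section 10 gives the same definition. Section 12.1 adds: "The primary outcome measure will be change score on the FACIT-fatigue subscale from randomization to the end of the study". Section 1.2 describes the primary comparison as one between changes in the two arms. None of these sections names a test or model, and none lists a covariate for the primary comparison.

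For the sample size, section 12 describes FACIT-F scores in cancer populations as normally distributed "with a standard deviation of 10 points". It then uses that figure to size a between-arm difference in change of 3.6 points, with 80% power at two-sided 0.05, and arrives at 122 per arm. It continues: "Assuming a 20% drop-out rate, approximately 150 patients per arm will be randomized". No SD of change and no baseline-to-follow-up correlation is given.

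The only covariate named in section 12 is in 12.4, under the secondary endpoints: "radiation therapy status (currently receiving RT vs. recently completed RT) will be included as a covariate in the multivariate analysis". Section 4.3 blocks randomization within site and section 12.3 stratifies by chemotherapy, but neither factor is carried into a primary model.

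**The concern.** The SD of a score and the SD of a change are different quantities, and they coincide only at a particular correlation between the two measurements. The plan takes the first and uses it as the second. A reader therefore cannot tell whether the stated 80% power applies to the comparison the plan describes. If the 5-week correlation is below about 0.5 (with equal SDs of 10), a raw-change comparison has less power than stated; if above, more.

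The week-0 FACIT-F is collected on every randomized patient. Adjusting for it cannot give a larger error variance than raw change, so an unadjusted comparison gives away precision on the main result. Leaving the primary model unnamed also allows the choice between adjusted and unadjusted analysis to be made after the data are seen.

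**Working it through.** **Inputs.** From section 12: difference 3.6 points, SD 10 (scores), two-sided alpha 0.05, power 0.80, 122 evaluable per arm, about 150 randomized, 20% drop-out. From section 10: test-retest reliability 0.82. Not in the documents: the correlation r between week-0 and follow-up FACIT-F, and the SD of change. A range of r is therefore assumed.

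**Step 1: reproduce the plan.** n per arm = 2 × (1.960 + 0.842)² × 10² / 3.6² = 121.1, rounded up to 122. The t-test version gives 122.1, and t-test power at 122 per arm is 79.97%. The stated 122 is right if 10 is the SD of the quantity compared. Drop-out: 122 / 0.8 = 152.5, against about 150 in the plan; 150 × 0.8 = 120 evaluable, at which power is 79.3%.

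**Step 2: what the SD must be.** The quantity compared is a change. With SD 10 at both times, SD of change = 10 × √(2(1 − r)). Setting this to 10 gives r = 0.5. The ANCOVA residual SD is 10 × √(1 − r²).

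**Step 3: power and n over a range of r** (t-test, SD 10 at both times, 3.6 points):

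| r | SD of change | ANCOVA residual SD | Power at 122 per arm: change vs ANCOVA | n per arm for 80%: change vs ANCOVA |
|---|---|---|---|---|
| 0.2 | 12.65 | 9.80 | 60% vs 82% | 195 vs 118 |
| 0.3 | 11.83 | 9.54 | 66% vs 84% | 171 vs 112 |
| 0.4 | 10.95 | 9.17 | 73% vs 86% | 147 vs 103 |
| 0.5 | 10.00 | 8.66 | 80% vs 90% | 123 vs 92 |
| 0.6 | 8.94 | 8.00 | 88% vs 94% | 98 vs 79 |
| 0.7 | 7.75 | 7.14 | 95.1% vs 97.5% | 74 vs 63 |
| 0.8 | 6.32 | 6.00 | 99.3% vs 99.7% | 50 vs 45 |

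With 120 per arm: r = 0.3, 65% vs 83%; r = 0.5, 79.3% vs 89%. At r = 0 ANCOVA with 120 per arm still has 79.3%.

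**Step 4: is the ordering general?** With baseline SD s1 and follow-up SD s2, var(change) = s1² + s2² − 2·r·s1·s2 and the ANCOVA residual variance is s2²(1 − r²). Their difference is (s1 − r·s2)², which is never negative. Raw change matches ANCOVA only when s1 = r·s2. The cost of adjustment is one degree of freedom per covariate, which is negligible with about 240 patients.

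**Step 5: effect of the entry rule.** Section 3.3.7 admits patients on a FACIT-F drop of 10 points or more, which alters the spread at randomization. A simple simulation took pre-radiotherapy, trigger and follow-up scores as trivariate normal with SD 10 and equal correlations, a mean drop to trigger of 0, 5 or 8 points, entry if the drop was at least 10, and the trigger score as baseline. Power at 122 per arm, by the correlation before selection:

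| Unselected r | Raw change | ANCOVA |
|---|---|---|
| 0.2 | 68–69% | 82% |
| 0.3 | 74–75% | 85% |
| 0.4 | 80–82% | 88% |
| 0.5 | 87–88% | 92% |

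At unselected r = 0.4 the baseline SD falls to 8.7–8.9 and the SD of change is 9.8–10.0. Under this model raw change reaches 80% at an unselected r of about 0.4 rather than 0.5.

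**Step 6: limit of the remedy.** ANCOVA still depends on the external SD. At SD 12 and r = 0.5 the SD of change is 12 × √1 = 12 and the residual SD is 12 × √0.75 = 10.39; power is 65% vs 77%.

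**The case against.** The strongest reply is that the plan defines an endpoint, not an unadjusted test. Regressing change on treatment and week-0 score gives the same treatment estimate as ANCOVA of the follow-up score, so a change endpoint is compatible with adjustment, and the analysis mentioned in 12.4 might be meant to cover the primary endpoint. The equivalence is correct. But section 1.2 states the primary comparison as one between changes, 12.4 sits under secondary endpoints, and baseline FACIT-F is named nowhere as a covariate. At best the primary model is unstated, and the same fix is needed.

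Second, no sizing error is shown. The arithmetic reproduces, the raw-change comparison is unbiased, regression to the mean affects both arms alike, and at r of 0.5 or more the planned n meets its target. All of this stands. If the test-retest figure of 0.82 in section 10 applied, raw change would have 99.7% power. That figure is not a correlation across five weeks of treatment and recovery, and the plan does not use it for sizing. Equally, nothing in the documents supports r of 0.2 to 0.3, where the gaps are largest; at 0.7 to 0.8 the gap is small.

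Third, the entry simulation is simplified: section 1.1 allows entry at any weekly assessment, and the scale runs from 0 to 52. A version with first crossing over six weekly looks and capped scores (assumed pre-radiotherapy mean 40, drift up to 5 points, SD 10 before capping) gives raw change about 80% at unselected r = 0.3, 85% at 0.4 and 91% at 0.5, against 88%, 91% and 94% for ANCOVA. So the correlation at which raw change reaches 80% depends on the model, at roughly 0.3 to 0.5. ANCOVA was better in every case.

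**Conclusion.** The concern holds. The primary effect is a raw change with no model or covariate stated, and the trial is sized with an SD attributed to single scores. The stated 80% power therefore depends on an SD of change of about 10 that the plan neither states nor justifies. With SD 10 at both times, 122 evaluable per arm and r between 0.3 and 0.7, raw change has 66% to 95% power and ANCOVA 84% to 98%. ANCOVA's advantage in error variance holds for any SDs and any r; its size depends on r, which the documents do not give.

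This is a matter of precision and of a checkable power statement, not of validity. Underpowering is not shown. The change should be made because it improves the precision of the primary result using data already collected.

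**What to change.** In 12.1, name the primary model: ANCOVA of end-of-treatment FACIT-F on treatment, adjusted for week-0 FACIT-F, site and prior chemotherapy, with radiotherapy status at randomization (already planned as a covariate in 12.4) added.

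Two definitions need settling with it:

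- **Follow-up score.** Section 1.1 ties outcome assessment to week 5 ("one at the conclusion of medication treatment for treatment outcome assessment and safety monitoring (week 5"), section 12.1 refers to the end of the study, and the intervention calendar in section 9 also has a week-9 FACIT-F. Use week 5 and make 12.1 agree.
- **Baseline score.** Section 5.3 says to "complete baseline fatigue questionnaire (unless completed within past week"), so a score from the preceding week can stand in. State which score is the week-0 value when that happens.

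In section 12, say that a residual SD of at most 10 gives about 80% power with 122 evaluable per arm (about 79% with the 120 left after 20% drop-out from 150), and more if baseline and follow-up are correlated. Show a range of r and SD beside it.

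As a clarification only, state in both 4.3 and 12.3 that randomization is blocked within site and stratified by chemotherapy.

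**Cost:** wording in sections 4.3, 12, 12.1 and 12.3. All the covariates are already collected, so no patients, visits or assessments are added.
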